#### 9.1.2 Number of subjects

Four hundred and fifty (450) randomized subjects are planned in total (approximately 150 subjects per group). It is expected that the screen failure rate will be around 70%. Therefore, approximately 1500 subjects will be screened in order to randomize 450 subjects into the study.

#### 9.1.3 Study region/location

The study will be conducted in approximately 130 investigational sites in the United States (US) and Canada. Additional sites will be identified, qualified and activated in case of recruitment issues. Recruitment will be competitive between countries and sites.

The COVID-19 situation has had a negative impact on the recruitment rate in our Phase 3 clinical trials. Therefore the Company may consider opening new sites outside the US and Canada.

## 9.2 ENTRY CRITERIA

### 9.2.1 Inclusion Criteria

1. The subject must provide written informed consent prior to any study related procedures.
2. The subject must be a female subject aged 18 years to 49 years inclusive.
3. The subject must have had her most recent surgical and – if available – histological diagnosis of pelvic endometriosis (laparoscopy, laparotomy, vaginal fornix or other biopsy) up to 10 years before screening.
4. The subject must agree to the washout intervals for prohibited therapies (if applicable).
5. The subject must agree to switch from her usual analgesic rescue medication to only those permitted by the protocol during the Screening, Treatment and Follow-up Period.
6. The subject has moderate to severe EAP during the screening period defined as:

- a. At the screening visit, a score of at least 2 for DYS and at least 2 for NMPP for the previous month assessed with the modified Biberoglu & Behrman (mB&B) scale.
- b. Over two full menstrual cycles (i.e. from day 1 of the first menstruation going over two spontaneous menstrual cycles up to the day before the next menstruation i.e. the third menstruation) finishing just before the baseline visit:
  - i. Mean overall pelvic pain scores of at least 4 on the 0–10 NRS over the 5 days with the highest score for each cycle separately, i.e. required for both cycles;
  - ii. At least two days with “moderate” or “severe” pain on the 0–3 VRS for pelvic pain over the days with uterine bleeding for each cycle separately, i.e. required for both cycles;
  - iii. At least two days with “moderate” or “severe” pain on the 0–3 VRS for pelvic pain over the days without uterine bleeding for each cycle separately, i.e. required for both cycles.
7. The subject is compliant with eDiary completion i.e. has completed at least 75% of days during the screening period.
8. The subject has regular menstrual cycles and the total length of the two screening menstrual cycles should be between 42 and 76 days inclusive.
9. The subject has a Body Mass Index (BMI)  $\geq 18 \text{ kg/m}^2$  at the screening visit.
10. If of childbearing potential, the subject agrees to use one of the following birth control methods during the Screening Period, the entire Treatment Period of the study and until 3 months after the end of treatment:
  - a. Sexual abstinence, if this is the subject's habitual practice and/or the subject is routinely abstinent from heterosexual intercourse,
  - b. Partner with a vasectomy with confirmed azoospermia,
  - c. Double non-hormonal barrier contraception such as condom or diaphragm each combined with spermicide.
11. If of non-childbearing potential, the subject must have had tubal ligation sterilization at least two months before the screening visit.
12. The subject is  $\geq 40$  years of age at the screening visit has a normal mammogram within 1 year before randomization.
13. The subject must be able to communicate well with the Investigator and research staff and to comply with the requirements of the study protocol.

### 9.2.2 Exclusion Criteria

To be eligible for inclusion in this study the subject must not meet any of the following criteria:

1. The subject is pregnant or breast feeding or is planning a pregnancy within the duration of the Treatment Period of the study.

2. The subject is less than 6 months postpartum or 3 months post-abortion/miscarriage at the time of entry into the screening period.
3. The subject has a surgical history of:
  - a. Hysterectomy,
  - b. Bilateral oophorectomy,
  - c. Vagotomy, bowel resection or any surgical procedure (including gastric surgery) that might interfere with gastrointestinal motility, pH, or absorption,
  - d. Any major abdominal surgery (including laparotomy for endometriosis) within 6 months or any interventional surgery for endometriosis performed within a period of 2 months before screening, or the subject is scheduled for a surgical abdominal procedure during the course of the study.
4. The subject had a tubal sterilization which was performed with ESSURE™.
5. The subject had endometrial ablation resulting in amenorrhea.
6. The subject has at least one ovarian endometrioma with a diameter of 7 cm or greater.
7. The subject is likely to require treatment during the study OR received treatment within a specified period prior to screening with any of the medications listed below:

a. GnRH antagonists	3 months
b. GnRH agonist injections/3-month depot injections	3/6 months
c. Danazol	3 months
d. Oral contraceptives and other sex hormones	1 month
e. Depot contraceptives	10 months
f. Selective Progesterone Receptor Modulators (SPRMs), Selective Estrogen Receptor Modulators (SERMs) and aromatase inhibitors	3 months
g. Long acting narcotics (i.e. requiring less than once daily dosing)	1 day
h. Systemic glucocorticoid treatments for acute diseases (not depot)	1 month
i. Medical (prescribed) marijuana	1 week
j. In situ copper intra-uterine device (IUD)	1 day
k. In situ IUD with progestogen	1 month
8. The subject is likely to use cannabinoids during the study washout, screening or treatment period.
9. The subject has required more than 2 weeks of continuous use of a narcotic analgesics for treatment of EAP within 6 months prior to Screening.
10. The subject received strong CYP3A4 inducers or inhibitors that (might potentially) interact with ABT within 1 month prior to randomization.

11. The subject has a contra-indication to ABT including:
  - a. Active deep vein thrombosis, pulmonary embolism, or history of these conditions;
  - b. Active or recent (e.g. within the past year) arterial thromboembolic disease (e.g. stroke, myocardial infarction);
  - c. Known, suspected, or history of breast cancer;
  - d. Known or suspected estrogen-dependent neoplasia;
  - e. Known protein C, protein S, or antithrombin deficiency, or other known thrombophilia disorders, including Factor V Leiden;
  - f. Migraine with aura;
  - g. History of porphyria;
  - h. Known hypersensitivity to the ingredients.
12. The subject has a history of or current systemic glucocorticoid therapy for treatment of chronic diseases (e.g. Systemic Lupus Erythematosus (SLE), rheumatic arthritis). Inhaled glucocorticoids for e.g. asthma are not considered systemic glucocorticoids.
13. The subject did not respond to prior treatment with GnRH agonists or GnRH antagonists for endometriosis.
14. The subject has alanine aminotransferase (ALT), aspartate aminotransferase (AST), total bilirubin levels or gamma-glutamyl transpeptidase (GGT) level  $\geq$  2 times the upper limit of normal and indicative of potential liver damage at Screening or Day 1 (subjects with abnormalities at Day 1 will be withdrawn from study at reception of the results).
15. The subject has clinically significant abnormal ECG, or ECG with QTc using Fridericia's correction formula ( $QTcF > 450$  msec) at Screening or Day 1 (prior to dosing).
16. The subject has a known positive human immunodeficiency virus (HIV) or viral Hepatitis serology.
17. The subject has abnormal uterine bleeding of undiagnosed cause.
18. The subject had/has clinically significant findings from a Papanikolaou (PAP) smear test performed within the past 12 months or at the screening visit which will require surgical intervention (e.g. Loop electrosurgical excision procedure (LEEP) or cervical conization).
19. The subject has chronic pelvic pain that, in the opinion of the Investigator, is not caused by endometriosis and requires chronic analgesic or other chronic therapy which would interfere with the assessment of EAP (e.g., interstitial cystitis, presumptive adenomyosis, fibroids, non-endometriosis-related pelvic adhesive disease, post-tubal ligation or irritable bowel syndrome).
20. The subject has any other clinically significant gynecological condition identified during screening transvaginal ultrasound (TVUS) or endometrial biopsy which might interfere with the study efficacy and safety objectives (e.g. endometritis, endometrial hyperplasia). However, uterine fibroids (as long as uterus size  $\leq$  12 weeks, i.e. equivalent gestational weeks) and adenomyosis are allowed provided they do not interfere with the assessment of EAP (see previous criterion).

21. The subject has any known condition, including findings in the medical history or in the screening assessments, which in the opinion of the Investigator constitutes a risk or a contraindication to the participation of the subject in the trial or that could interfere with the trial objectives, conduct or evaluation.
22. The subject has a history of, or known, osteoporosis, hyperparathyroidism or other metabolic bone disease.
  - a. Screening DXA results of the lumbar spine (L1–L4), femoral neck, or total hip BMD showing a Z-score  $\leq -1.5$
  - b. Any condition that would interfere with obtaining adequate DXA measurements (e.g. weight [ $> 300$  pounds or 136 kg], history of spinal surgery, spinal hardware, severe scoliosis)
  - c. Intercurrent bone disease
  - d. History of hip fracture
  - e. History of pathologic or compression fractures
  - f. History of bilateral hip replacement
23. The subject has a mental condition rendering her unable to understand the nature, scope and possible consequences of the study, or evidence of an uncooperative attitude.
24. The subject has current problem with alcohol or drug abuse (including painkiller abuse).
25. The subject has been administered with any experimental drug in the 12 weeks before screening and/or has been randomized in Edelweiss 3 (Phase III) study protocol No. 18-OBE2109-003.
26. The subject has calcium level above the upper limit of normal range at screening, which is confirmed on repeat fasting testing at Screening.
27. The subject has a history of, or active malignancy (with or without systemic chemotherapy) (except treated basal carcinoma of the skin which is not an exclusion criterion).
28. The subject has a history of attempted suicide and/or a history of, or known major psychiatric disorders that are not well controlled.

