#### 10.2.2.1 *Baseline visit: Day 1*

If the subject has successfully completed all screening assessments and is between the first and seventh day (inclusive) of her menstruation, she will go to the investigational site for the following evaluations and tests **before drug administration**:

- eDiary eligibility data review
- ePRO and ClinRO completion, ideally before any other procedures or assessments: EHP-30, HRPQ, HRUQ, PSIQ, SSIQ, PROMIS, EQ-5D-5L, specific monthly severity questions, mPGIS (anchors must be completed last)
- Completion of the paper C-SSRS questionnaire “Baseline” version, if not already completed during screening period (see Appendix R)
- Screening DXA results review
- Screening lab results review
- Screening endometrial biopsy results review (randomization will not be postponed if the results of the endometrial biopsy performed during the screening period are not available on Day 1)

- Previous and concomitant treatments recording
- AE recording
- ECG
- Vital signs (BP and heart rate)
- Urine pregnancy test
- Urinary protein dipstick
- Fasting (overnight) blood samples for haematology, coagulation parameters, chemistry, lipids, glucose, hormones and bone biomarkers, prior to the first administration of study treatment, and after confirmation of the subject's eligibility (considering the invasive nature of this procedure).

Upon confirmation of inclusion/exclusion criteria, the subject will be randomized to one of the three treatment groups and will be provided with the study drugs (1 kit of linzagolix/placebo and 1 kit of ABT/placebo) and provided/prescribed with permitted analgesics as well as vitamin D and calcium supplements. The subject will be instructed on how to take the study drugs and analgesics, and advised to take the provided vitamin D and calcium daily. The subject will be provided/prescribed as necessary with analgesics and vitamin D/calcium supplements at each subsequent visit to cover requirements until the end of the follow-up period.

The subject will take her first dose of study medication at the study site. The exact time of dosing (hour/minute) will be recorded in eCRF.

**After drug administration**, the following procedures will be performed:

- ECG at about the same time as but before the post-dose PK sample
- Post-dose PK sample taken at least 1.5 h after treatment administration. The exact time of dosing and of PK sampling (hour/minute) will be recorded in the eCRF.

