#### **10.7.2.1 Discontinuation criteria**

During the course of the study, the subject may be discontinued for the following reasons:

- **Adverse Event:** Includes clinically significant new or worsening existing condition as judged by the Investigator. Document in the AE form.
- **Subject's Request:** Consent withdrawal, subject moved, schedule conflicts, etc. Specify the reason in the comment section of the eCRF Exit Form.
- **Protocol Violation:** Major protocol violation which may affect the subject's safety. Specify the protocol violation in the comment section of the eCRF Exit Form.
- **Lost to Follow-up:** Document with at least two phone calls and a certified letter requesting return receipt without response. Document in the comment section of the eCRF Exit Form.
- **Pregnancy:** Subjects that have been exposed to study treatment and who become pregnant during the Treatment Period will be immediately withdrawn from treatment. Pregnancies that have been exposed to study treatment and occurred up to Month 3 FU visit, or started up to 4 weeks after treatment discontinuation in case of early withdrawal will be followed up for pregnancy and neonatal outcomes at birth. Any pregnancy must be reported with the Pregnancy Surveillance Form (see section 12.6).
- **Other:** Specify in the Comments section in the eCRF Exit Form. This reason should only be used if the reason for discontinuation is not better accounted for by another category.

**Discontinuation Rules at Day 1:** Subjects presenting with ALT, AST, GGT or total bilirubin  $\geq 2$  ULN should be discussed with the Sponsor and may have to discontinue study treatment if these results are indicative of liver involvement.

Subjects presenting with a clinically significant finding in the biopsy sample collected at screening and who have completed Day 1, will have to discontinue study treatment.

Subjects who have a serum calcium level at Day 1 above 2.9 mmol/L and who have completed Day 1, should have calcium supplements interrupted. If serum calcium level at Day 1 is above 3.1 mmol/L calcium supplements **and study treatment** are to be interrupted. A repeat test of this parameter within 2 weeks under fasting conditions is to be performed. If the results of the repeat remain above 2.9 mmol/L, study treatment should definitively be discontinued and the subject should be advised to consult an endocrinologist for further evaluation.

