#### 10.7.3 Subject Replacement

Discontinued subjects who did not receive the study drug may be replaced.

Additional subjects may be recruited due to subjects who were discontinued due to ALT, AST, GGT or total bilirubin  $\geq 2$  times the upper limit of normal at Day 1, or due to a clinically significant biopsy finding at Day 1 (treatment start), or due to high calcium level at Day 1.

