### **12.1.2 Abnormal laboratory findings and other objective measurements**

Abnormal laboratory findings and other objective measurements (e.g. vital signs) must be reported as an AE only if assessed by the Investigator as “clinically significant” e.g. meeting at least one of the following conditions:

1. The abnormality suggests a disease and/or organ toxicity AND this abnormality was not present at the screening visit or is assessed as having evolved since the screening visit.
2. The abnormality is a Serious Adverse Event.
3. The abnormality results in discontinuation of the IMP.
4. The abnormality requires medical intervention or concomitant therapy.

The Investigator must initial and date each laboratory report/eCRF page and note directly on the report/eCRF page whether or not each out-of-range laboratory result is clinically significant. The outcome of this assessment will be reported using an AE or SAE form, as appropriate.

When reporting an abnormal finding for laboratory parameters or other objective measurements on the AE page of the eCRF, a clinical diagnosis should be recorded rather than the abnormal value itself, if available (for example, “anaemia” rather than “decreased red blood cell count”).

For all of these AEs, whether or not related to the treatment, the laboratory test(s) will be followed-up as appropriate.

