### 12.2.3 Reporting of Adverse Events

Complete and accurate data on all AEs experienced for the duration of the reporting period, as defined in section 12.5, will be reported on an ongoing basis in the AE pages of the eCRF.

It is important that each AE report includes a description of the event, whether it is considered serious (and if so the criterion satisfied), its duration (onset and resolution dates), its severity, its relationship to the IMP(s), any other potential causality factors, any treatment given or other action taken (including dose modification or discontinuation of the IMP) and its outcome.

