Baseline dysmenorrhea, non-menstrual pelvic pain, analgesic use and uterine bleeding will be based on the calculation from daily e-diary data from menstrual cycles during the screening period. The screening period must cover at least two full menstrual cycles. The following rules apply to select the two baseline menstrual cycles for assessment of eligibility and baseline:

- If only two full screening cycles are covered prior to Day 1: those two screening cycles should be used for both eligibility assessment and baseline calculation.
- If 3 full screening cycles are covered during the screening period, for logistical reasons, as allowed per protocol: "If for logistical reasons beyond her control, the subject is unable to come to the clinic for Day 1 within the acceptable time window (1st to 7th day inclusive of the cycle) then the subject will be allowed to start Day 1 in the following cycle (again on the 1st to 7th day of the cycle). In this case, the eligibility assessments should be assessed based on the first two cycles only"; the two first screening cycles should be used for both eligibility assessment and baseline calculation.
- If more than 3 full screening cycles are covered during the screening period: the two last menstrual cycles prior to the baseline visit will be considered for both eligibility assessment and baseline calculation.
- Due to possible technical issues with the e-diary device, some data during the screening menstrual cycle may not be collected properly. Consequently the menstrual cycles may not be considered as valid for assessment of eligibility and baseline and other cycles than first and second ones might be used on a case-by-case basis. The sponsor will provide an excel file listing all the menstrual cycles that were used for measurement of eligibility and baseline.

The baseline DXA assessment will be derived as the latest non-missing DXA assessment with acceptable quality (accepted="Yes") prior to the Baseline visit or the first non-missing assessment

Sponsor:	ObsEva		
Protocol:	18-OBE2109-002		
Document Version No.:	1.0	Document Date:	18-MAY-2021

with acceptable quality (accepted="Yes") done up to 10 days after the baseline visit if there is no assessment prior to baseline.

For other data not specified before, baseline will be defined as the data most recently collected prior to the first dose of IMP.

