4.8.1.2. Compliance

Lingazolix/Placebo Grey blister (200 mg or matching placebo), Lingazolix/Placebo Pink blister (75 mg or matching placebo) and Add-back therapy compliance from the study treatment accountability page among the Day 1- End of main study treatment period will be summarized by treatment group.

If Lingazolix/Placebo and Add-back therapy compliances from accountability data are missing, compliance will be computed from daily diary data.

Compliance will be computed as the number of days with pink tablet/grey tablet/Add-back capsule taken *100 divided by the number of days in the period (Month 6 visit date/withdrawal date - Day 1). Data from “Today” will be used primarily. If data from today is missing, date from “Yesterday” will be considered. If the e-diary is not completed for a day (neither “Today” nor “Yesterday”), it will be assumed that no intake of drug was taken on that day.

Study treatment overdose and misuse will be reported in a listing.

Compliances will be reported in a listing.

Sponsor:	ObsEva		
Protocol:	18-OBE2109-002		
Document Version No.:	1.0	Document Date:	18-MAY-2021

4.8.2. **Adverse Events**

Adverse events will be coded using the Medical Dictionary for Regulatory Activities (MedDRA) and displayed in tables and listings using System/Organ/Class (SOC) and Preferred Term.

Analyses of adverse events will be performed for those events that are considered treatment emergent (TEAEs), where treatment emergent is defined as AEs with a start date on or after the first dose of study drug through 30 days after discontinuation of study drug or Month 6 visit date, or any event that was present at baseline but worsened in intensity or was subsequently considered drug-related by the investigator through the end of the study.

Adverse Event tables will be presented for the following periods: Day 1 to Month 6 (treatment period) and Month 6 to Month 6 FU (follow-up period) as defined in section 4.2.12.

Adverse events starting more than 30 days after end of treatment will be considered as post-treatment AE.

Note: if an adverse event started after or at Month 6 visit date and if the subject entered the extension period, this adverse event will not be displayed for the main study, but only for the extension study.

For each of these 2 study periods, an overall summary table will be prepared presenting, by treatment group and overall, the number and percentage of subjects with

- any AE,
- any TEAE,

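### A liver finding from the pre-dose Day 1 sample can be tabulated as treatment-emergent, because the SAP rule works by date and has no same-day provision

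*Protocol*

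**What the plan says.** **Timing.** Protocol 10.2.2.1 places the Day 1 bloods, chemistry included, before the first dose, which is taken at the site the same day. For the screening biopsy it adds that "randomization will not be postponed if the results of the endometrial biopsy performed during the screening period are not available on Day 1".

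**Stops after dosing.** Exclusion criterion 14 (Protocol 9.2.2) covers liver tests of at least 2 x ULN that suggest liver damage, and states that "subjects with abnormalities at Day 1 will be withdrawn from study at reception of the results". The Day 1 rules in Protocol 10.7.2.1 treat the same liver finding as a matter to discuss with the sponsor, with a possible stop. Women with a clinically significant screening biopsy finding "who have completed Day 1, will have to discontinue study treatment". For calcium, a Day 1 value above 2.9 mmol/L interrupts supplements, and one above 3.1 mmol/L also interrupts study drug. A permanent stop follows only if a repeat test within 2 weeks is still above 2.9 mmol/L.

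**Reporting.** Under Protocol 12.1.2 an abnormality is an AE only if the investigator judges it clinically significant. One listed condition is "The abnormality results in discontinuation of the IMP". Protocol 12.2.3 asks for onset and resolution dates and mentions no onset time.

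**Analysis.** In SAP 4.8.2, "treatment emergent is defined as AEs with a start date on or after the first dose of study drug", running to 30 days after stopping. Protocol 13.5.5 uses the same start. For data without a rule of their own, which includes the laboratory data, SAP 4.2.11 says that "baseline will be defined as the data most recently collected prior to the first dose of IMP".

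**The concern.** For the liver tests, one blood sample has two roles. In the laboratory tables it is the pre-treatment reference value. In the AE tables an event arising from it can count as emerging on treatment and as a reason for permanent discontinuation. A sample drawn before the first tablet cannot show an effect of that tablet.

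The protocol treats these women as a separate group. Section 10.7.3 begins "Additional subjects may be recruited due to subjects who were discontinued due to ALT, AST, GGT or total bilirubin" and ties the abnormality to Day 1. It gives the same allowance for a biopsy finding or high calcium at Day 1.

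The affected outputs are the tables of TEAEs and of TEAEs leading to permanent discontinuation (Tables 14.3.1.2.1 and 14.3.2.3.1). After early termination the SAP drops the efficacy and pharmacokinetic analyses, so the safety tables are the main product of the trial. Liver, calcium and endometrial findings each have stopping rules in this protocol.

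**Working it through.** The plan gives no figure to reproduce here. The check applies the stated rule to each possible onset date.

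**Rule (SAP 4.8.2, first limb).** An AE is treatment-emergent if first-dose date ≤ AE start date ≤ last-dose date + 30 days. Take Day 1 as the first dose. The other days below are illustrative.

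| Source of the AE | Onset date used | Result |
|---|---|---|
| Day 1 chemistry | Collection, Day 1 | TEAE |
| Day 1 chemistry | Result received, e.g. Day 3 | TEAE |
| Screening biopsy | Collection, e.g. Day -20 | Not TEAE |
| Screening biopsy | Result received, e.g. Day 5 | TEAE |
| Screening biopsy | Entered as medical history | No AE |

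If the onset day is missing and the month is that of the first dose, SAP 4.2.8.1 imputes the earlier of the first-dose date and the AE resolution date. That again gives a TEAE unless the event resolved before dosing.

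**Permanent-discontinuation row.** The SAP does not name the variable behind this row. I assume it is the action-taken field in Protocol 12.1.1:

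- *Drug withdrawn*: the event enters the row.
- *Not applicable*, a code offered for AEs that began before dosing: the event stays out of this row. It remains in the any-TEAE row, because the TEAE definition does not use this field.
- *Drug interrupted*: the event is not a permanent discontinuation. This is the action for a Day 1 calcium above 3.1 mmol/L.

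**By finding.**

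- *Liver*: the sample is pre-dose, and both plausible dates give a TEAE.
- *Calcium*: an AE dated Day 1 is a TEAE, but the Day 1 value alone never produces a permanent stop, because the repeat test comes after dosing.
- *Biopsy*: a TEAE arises only if the finding is reported as an AE dated Day 1 or later. Protocol 12.1.3 sends screening results to medical history. Protocol 10.7.3, however, describes the biopsy finding as being at Day 1, and no section fixes the date to use.

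**Size per woman.** Women dosed and then stopped remain in the Safety Analysis Set (SAP 3.1), so each adds 1/n to her arm's row:

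- Planned n = 150: 1/150 = 0.67 percentage points.
- SAP 1.2 says only that far fewer were randomized than planned. Assuming n = 20 to 60: 1/20 = 5.0, 1/30 = 3.3, 1/60 = 1.7 percentage points.

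**The case against.** The strongest reply is that the protocol already separates pre-dose findings. Section 12.1.1 says that events before the first dose are not AEs in the strict sense and asks for a judgement between AE and baseline condition. Section 12.1.3 puts screening results in medical history. The action-taken list has a code for events that began before dosing. Section 12.1.2 makes reporting depend on clinical significance. In addition, SAP 4.8.2 plans no AE hypothesis tests and lists every AE, and the disposition table gives reasons for stopping before Month 3. Imputing uncertain onset dates toward treatment-emergent also suits a cautious safety analysis.

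Much of this stands for the biopsy. For calcium, the permanent stop has a post-dose basis. The lack of an AE onset time is an inference from Protocol 12.2.3, since the eCRF itself is not in the documents.

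It does not settle the liver case. Section 12.1.1 still sends post-consent, pre-dose events to the AE form. Section 12.1.3 names the screening visit(s), not Day 1. The action code does not affect TEAE status. The SAP limb on baseline events that worsen is joined to the date limb by *or*, so it adds events and removes none. Caution about unknown dates does not justify misclassifying an event whose sample is known to be pre-dose.

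**Conclusion.** The point holds for Day 1 liver tests. If the finding is reported as an AE, the date rule makes it treatment-emergent on either plausible onset date, and nothing in the SAP prevents this. Entry in the discontinuation row depends on how the action taken is coded. Calcium is affected in the any-TEAE row. The biopsy is affected only if the finding is reported as an AE dated Day 1 or later.

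A reader might infer three stronger things that the documents do not support:

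- That all three Day 1 rules always yield TEAEs leading to discontinuation. Sections 10.7.2.1 (calcium repeat), 12.1.3 and the action codes in 12.1.1 rule that out.
- That the comparison with placebo is biased. The samples precede dosing in a randomized trial, so balance is expected on average, although it is not assured with few events. What rises is the absolute rate.
- That many women are involved. Section 10.7.3 only permits extra recruitment and gives no number.

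The size is therefore per woman: 0.67 points at 150 per arm, or 5.0 to 1.7 points at an assumed 20 to 60. The total effect is unknown. A correction is worthwhile because it is cheap and these tables are now the main output.

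**What to change.** In SAP 4.8.2, state that an AE whose only source is a Day 1 pre-dose laboratory sample or a screening biopsy is a pre-treatment AE and not a TEAE, whether it is dated Day 1 or at receipt of the result. Make an exception if it worsens after the first dose or a post-dose test confirms it as a new finding.

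List these events. Show liver and biopsy stops under the Day 1 rules as their own row in the disposition table. Keep calcium stops confirmed by a post-dose repeat test in the discontinuation table, with a footnote giving the Day 1 value.

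The cost is one SAP sentence, one disposition row, one footnote, and a blinded manual review of AEs dated Day 1 or at receipt of a pre-dose result. The drawback is that a few events need individual classification.

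Separately, Protocol 9.2.2 (criterion 14: withdrawal from the study when results arrive) and Protocol 10.7.2.1 (discussion with the sponsor and a possible stop of study treatment) describe different consequences of the same liver finding and must be reconciled.
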